### **Study design:**

Prospective randomized controlled study. The method of randomization was a sealed envelope technique.

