### **Sample size technique:**

Sample size was calculated using G\*Power (3.1.9.4) software for windows using Fisher analysis test. A total sample size of 132 participants was estimated for 95% power,  $\alpha$ - error probability 0.05. Analysis of data was performed using IBM SPSS v. 25 (Statistical Package for Social science) for Windows.

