### **Study procedure:**

- Demographic and medical history for all patients included in this study will be recorded.
- Complete physical examination for all patients included in this study will be taken.
- Basic routine investigation for all patients included in this study will be measured as Complete blood Count test (CBC), blood pressure and temperature.
- Improvement of signs and symptoms after the end of antibiotic course as temperature.
- **Renal function** tests will be measured **before** patients received colistin or tigecycline and **after 72 hours from first dose**:

- Serum creatinine level (scr).
- **Hepatic function** tests will be measured **before** patients received colistin or tigecycline and **after 72 hours from first dose**:
  - Alanine transaminase (ALT)
  - Aspartate transaminase (AST)
  - Serum total bilirubin (TBIL)
- **14 days Survival rate after starting colistin or tigecycline will be recorded.**
- The severity of the illness will be assessed by using the Acute Physiology and Chronic Health Evaluation II (APACHE II) scoring system will be calculated.(Wu et al., 2022).

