### **Statistical analysis:**

All statistical analysis will be performed by using SPSS version 23. The demographic and clinical characteristics of patients will be expressed as mean  $\pm$  standard deviation (SD). Student's t-tests or Mann-Whitney tests will be used to compare between groups. Chi-square tests or exact tests (Fisher's exact test or likelihood ratio test) will be used to detect the existence of association between variables.

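### APACHE II is collected without a time point, and the stated analysis does not adjust 14-day survival for it: a cheap gain in precision and interpretability is missed

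*Protocol*

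**What the plan says.** Under Study procedure, serum creatinine and the liver tests are each to be measured before treatment and 72 hours after the first dose. Survival is dated too: "14 days Survival rate after starting colistin or tigecycline will be recorded". The last item in that list is "The severity of the illness will be assessed by using the Acute Physiology and Chronic Health Evaluation II (APACHE II) scoring system". It names no day, visit or reference event.

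Under Study design, allocation is described in one sentence: "The method of randomization was a sealed envelope technique".

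Under Statistical analysis, three statements cover everything planned. Patient characteristics are descriptive: "The demographic and clinical characteristics of patients will be expressed as mean" with its standard deviation. Two-group comparisons follow: "Student's t-tests or Mann-Whitney tests will be used to compare between groups". For categorical data, "Chi-square tests or exact tests (Fisher's exact test or likelihood ratio test) will be used to detect the existence of association between variables". No regression model or covariate is named. Survival is not named there, and no outcome is called primary.

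**The concern.** Survival over 14 days in intensive care is likely to depend on how ill the patient was at entry, and APACHE II is the only severity score that the protocol names. To describe the arms at baseline, or to serve as a covariate, it must be fixed before treatment can affect it. As written, a score at admission to intensive care, just before the first dose or at 72 hours would each comply, and patients could be scored at different points.

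A later score is a problem because, by its own name, APACHE II draws on acute physiology. The Introduction lists nephrotoxicity among colistin's reported side effects, and Study procedure treats temperature as a sign of improvement. Physiology measured after dosing may therefore already reflect the drug. Adjusting for such a score could remove part of the effect under study. Timing is an instruction for data collection, and no later analysis document can turn a post-dose score into a baseline one.

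At stake are the precision of the survival comparison and the ability to interpret it if the arms differ in severity.

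**Working it through.** **1. The plan's own figure.** For a two-sided Fisher's exact test of 0.58 against 0.261 at alpha 0.05, full enumeration at 66 per group gives power 0.95011 and actual alpha 0.03161. The Sample size calculation states 0.9501125 and 0.0316077. At 65 per group power is 0.9491, so 66 is the minimum. The figure is right, and nothing below changes it. The protocol does not say which outcome these two rates describe.

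**2. Size of chance imbalance, in SD units.** This needs only the 66 per arm. The SE of the standardised difference is sqrt(2/66) = 0.174. The chance of a difference above 0.20 SD is 25%, above 0.25 SD 15%, above 0.34 SD 5%, and above 0.50 SD 0.4%.

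**3. The same in points and in mortality.** Assumptions, none of them in the protocol: APACHE II SD 6 to 8, log-odds of death 0.05 to 0.10 per point, 14-day mortality 40%.

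- 95% range of imbalance = 1.96 × SD × sqrt(2/66): ±2.05 points (SD 6) to ±2.73 points (SD 8).
- Approximate risk shift = 0.4 × 0.6 × slope × imbalance: 0.24 × 0.05 × 2.05 = 0.025, up to 0.24 × 0.10 × 2.73 = 0.066.
- SE of the unadjusted risk difference = sqrt(2 × 0.24/66) = 0.085, so its 95% range is ±0.167.

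The shift lies inside that range. Its share of the variance is (0.025/0.167)² = 2% to (0.066/0.167)² = 16%. It is part of the sampling error that the test already allows for, and is not added to it.

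**4. Outcome variance explained by a baseline score.** Normal score, logistic risk, 40% mortality, with the slope range widened to 0.12:

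| SD | 0.05 per point | 0.08 | 0.10 | 0.12 |
|---|---|---|---|---|
| 6 | 2.1% | 5.0% | 7.5% | 10.2% |
| 7 | 2.8% | 6.6% | 9.7% | 13.0% |
| 8 | 3.6% | 8.3% | 12.1% | 16.0% |

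As a rough equivalent in patients, 1/(1 − R²) − 1 runs from 2% (R² 0.021) to 19% (R² 0.160).

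**5. Error rate and power by simulation.** There were 3,000 trials per setting at 66 per arm, with assumed log-odds of 0, 0.5, 0.8 and 1.1 per SD of the score. The assumptions in step 4 correspond to 0.05 × 6 = 0.30 up to 0.12 × 8 = 0.96 per SD.

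- No treatment effect: Fisher rejects in 0.025 to 0.035 of trials, the adjusted logistic model in 0.044 to 0.054.
- 0.58 against 0.261: Fisher about 0.95; adjusted 0.97 to 0.99 for a prognostic score (0.5 to 1.1 per SD).
- 0.50 against 0.30 (an assumed smaller effect): Fisher 0.57 to 0.60; adjusted 0.67 to 0.74 for a prognostic score.

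Part of that gain comes from leaving Fisher's conservative test. With a score of no prognostic value, the switch alone moves power from 0.607 to 0.669, or 6.2 points. In the last setting the total gain is 8.4 points at 0.5 per SD (0.583 to 0.667) and 14.4 at 1.1 (0.598 to 0.742). About 2 to 8 points are therefore due to the score itself. Each simulated power near 0.6 has a standard error of about 0.9 points.

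**The case against.** The strongest reply is that covariates and models are usually chosen in a statistical analysis plan, which is not at hand. Missing adjustment alone would not make a finding. That stands, and it is why the dating of the score comes first here. The analysis part is a suggested improvement on what is written: the Statistical analysis section presents itself as covering all analyses and lists unadjusted tests only.

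A reader might infer three stronger things that the protocol does not support.

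- *That the score has no use.* The descriptive summary and group comparison of clinical characteristics could include it, though it is not named there.
- *That the survival comparison is biased or its error uncontrolled.* Randomisation makes the unadjusted test valid, and the simulated type I error confirms this. Among the roughly 5% of trials with an imbalance above 0.34 SD, the unadjusted error was about 0.03 to 0.08. That rests on about 150 trials per setting and is too imprecise to build on.
- *That allocation is known to be unstratified and should be stratified.* The protocol is silent on stratification. A trial of 132 patients at one site does not need it, and an adjusted analysis gains most of what it would offer.

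Adjustment also has limits. A linear term captures only the severity that APACHE II measures in that form, and patients without a score need a stated rule.

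**Conclusion.** The point holds as a minor one. The time point is missing on the face of the protocol, in a list that dates its laboratory tests and survival. The stated analysis makes no use of the score in the survival comparison. The cost is lost precision and a harder reading of an unbalanced trial; validity is not affected. The size is uncertain: about 2% to 16% of outcome variance, depending wholly on the assumed SD, slope and mortality. If the slope is near 0.05 per point, the gain is only about 2% to 4%. At the planned difference power is already 0.95, so the benefit matters mainly if the true difference is smaller. The sample size is unaffected.

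**What to change.** **Study procedure.** State that APACHE II is calculated for every patient from the latest values available before the envelope is opened, and that the date and time are recorded.

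**Statistical analysis.** Add a prespecified analysis of 14-day survival: a logistic model with treatment and APACHE II as a continuous covariate, reported as a standardised risk difference with a 95% confidence interval. Keep the unadjusted test beside it, say in advance which of the two carries the conclusion, and state how a missing score is handled.

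**Cost.** One sentence on timing, one regression with a standardisation step, and the discipline of scoring before allocation. No extra patients or tests are needed, because the score is already planned. The timing must be settled before patients are scored, since it cannot be repaired afterwards.

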### **Statistical analysis:**

All statistical analysis will be performed by using SPSS version 23. The demographic and clinical characteristics of patients will be expressed as mean  $\pm$  standard deviation (SD). Student's t-tests or Mann-Whitney tests will be used to compare between groups. Chi-square tests or exact tests (Fisher's exact test or likelihood ratio test) will be used to detect the existence of association between variables.

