## **II. Aim and objectives:**

Objective from this study to compare the clinical outcomes and safety between colistin and tigecycline for multi-drug resistant gram negative bacteria.

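### The tests named for continuous values ignore the baseline creatinine and liver tests already scheduled; log-scale ANCOVA would use them and needs no extra data

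*Protocol*

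**What the plan says.** The aim (Protocol, section II) is to "compare the clinical outcomes and safety between colistin and tigecycline for multi-drug resistant gram negative bacteria", so safety is one of its two stated parts. The design is given as "Prospective randomized controlled study".

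Under Study procedure, serum creatinine and three hepatic tests (ALT, AST, total bilirubin) are each measured before treatment and again "after 72 hours from first dose".

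The Statistical analysis section is the only text on analysis methods apart from the sample size. For continuous values it states that "Student's t-tests or Mann-Whitney tests will be used to compare between groups". For categorical variables it states that "Chi-square tests or exact tests (Fisher's exact test or likelihood ratio test) will be used to detect the existence of association between variables". No covariate, regression or other baseline adjustment appears anywhere in the protocol. The section does not assign a test to each laboratory variable, and it does not say whether the 72-hour value or the change from baseline would be compared.

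**The concern.** Each patient has a pre-treatment value of the same laboratory variable, and in most settings that value predicts the 72-hour value. A t-test or Mann-Whitney test on the 72-hour value discards it. The same tests on the change use it, but with a fixed coefficient of one, which is generally not the best weight. ANCOVA estimates the weight from the data.

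The introduction names nephrotoxicity for colistin and hepatic effects for tigecycline. These four values are the only renal and hepatic measurements scheduled after baseline. The sample size rests on a comparison of two proportions, so precision for the continuous laboratory comparisons was not planned. What is at stake is the width of the renal and hepatic safety intervals.

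**Working it through.** **Inputs from the protocol.** 66 patients per group, 1:1 allocation, two-sided 5% level. The sample size reproduces: full enumeration of Fisher's exact test for 0.58 against 0.261 at 66 per group gives power 0.9501 and actual alpha 0.0316, as stated. It concerns proportions and is not affected by this point.

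**Inputs assumed.** The correlation r between baseline and 72-hour values (0.3, 0.5, 0.7); the ratio k of the 72-hour SD to the baseline SD (1 unless stated); for power, a shift of 0.4 SD. The protocol gives none of these. The covariance is taken as the same in both arms.

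**Variance of the group difference**, in units of the baseline variance and with the common factor 2/66 left out:
- 72-hour value: k²
- change: k² + 1 − 2rk
- ANCOVA: k²(1 − r²)

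The first minus the third is k²r². The second minus the third is (1 − rk)². Neither can be negative, so ANCOVA is at least as precise as either t-test, apart from the degree of freedom spent on the slope. That costs an expected factor of 1 + 1/(132 − 4) = 1.0078, about 0.8% of variance.

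**Share of variance removed by ANCOVA** (before the 0.8% unless marked net):

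| Comparator | r = 0.3 | r = 0.5 | r = 0.7 |
|---|---|---|---|
| 72-hour value, any k: r² | 9% | 25% | 49% |
| the same, net | 8% | 24% | 49% |
| change, k = 1: (1 − r)/2 | 35% | 25% | 15% |
| the same, net | 34% | 24% | 14% |
| change, k = 0.8 | 50% | 43% | 37% |
| change, k = 1.25 | 22% | 11% | 2% |
| change, k = 1.5 | 13% | 4% | 0% |

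Example for k = 1.25, r = 0.5: the change has 1.5625 + 1 − 1.25 = 1.3125 and ANCOVA 1.5625 × 0.75 = 1.1719, so 1 − 1.1719/1.3125 = 11% is removed. Against the 72-hour value, break-even is at r² = 1 − 1/1.0078 = 0.0078, that is r of about 0.09.

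**Detectable difference at 80% power** (noncentral t, degree-of-freedom cost included): 0.491 SD for the t-test on the 72-hour value; 0.471, 0.427 and 0.352 SD for ANCOVA at r = 0.3, 0.5 and 0.7.

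**Simulated power with skewed values** (lognormal, log SD 0.5 and 0.8, k = 1, r and the 0.4 SD shift on the log scale, 20,000 runs per cell; ranges cover both SDs):

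| Analysis | r = 0.3 | r = 0.5 | r = 0.7 |
|---|---|---|---|
| Mann-Whitney, 72-hour value | 60–61% | 60% | 60% |
| Mann-Whitney, change | 46–48% | 59–60% | 80–82% |
| t-test, log 72-hour value | 62–63% | 62–63% | 62% |
| ANCOVA on logs | 66–67% | 75% | 89% |

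Log ANCOVA gains about 6, 15 and 29 points over Mann-Whitney on the 72-hour value. About 4, 12 and 27 of these come from the baseline, judged against the t-test on the log 72-hour value; the other 2 or so come from the move to a log-scale parametric test. Type I error of log ANCOVA was 4.8–5.3%.

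**Why the scale matters.** In a smaller simulation with stronger skew (log SD 1.0, 800 runs per setting) at r = 0.3, raw-scale ANCOVA had 46% power, Mann-Whitney on the 72-hour value 62% and log ANCOVA 67%. At r = 0.7, raw-scale ANCOVA had 67%, Mann-Whitney on the change 79% and log ANCOVA 91%.

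**The case against.** The strongest objection is scope. The named tests are valid, covariate adjustment of laboratory values is often left to the SAP, and an SAP that is not at hand may provide it. This does not remove the point. The protocol is not silent: it names the tests, and an SAP that used ANCOVA would depart from the protocol's own sentence.

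Second, the sentence on t-tests follows one about demographic and clinical characteristics and is not tied to the laboratory values. If renal and hepatic safety is reported only as event proportions, the point does not apply. That limit stands. If the four values are compared as continuous outcomes, however, these are the only tests the protocol offers.

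Third, the gain depends on the comparator and on assumed quantities. Against the change, which is a natural reading of before-and-after data, the normal-approximation power at r = 0.7 and k = 1 is 84% for the t-test and 90% for ANCOVA, a much smaller gain than against the 72-hour value. At k = 1.5 and r = 0.7 the gain is 0.2% of variance, and after the 0.8% cost ANCOVA is marginally worse. This stands as a limit on size; the worst loss is under 1% of variance.

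Fourth, ANCOVA must be on the log scale to be safe with skewed values, and a ratio of geometric means is a different summary from a difference in means or ranks. Both are true. The recommendation depends on the log scale, and the change of summary should be made knowingly.

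**Conclusion.** The point holds as an improvement in efficiency, not as the correction of an error. The named tests are unbiased under randomisation, but for continuous comparisons of creatinine, ALT, AST and bilirubin they make no use, or a generally suboptimal use, of a baseline that is already collected. For assumed correlations of 0.3 to 0.7, the net variance saving is 8% to 49% over the 72-hour value and, with equal SDs, 34% to 14% over the change. The saving over the change shrinks towards nil when r times the SD ratio approaches one.

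The direction rests on a common covariance in both arms and an analysis on the log scale. The size rests on a correlation and an SD ratio that the protocol does not give. Comparisons of proportions are not affected. The change is worth making because it is cheap and the possible loss is negligible.

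**What to change.** Add one sentence to the Statistical analysis section, before outcome data are examined by arm: where creatinine, ALT, AST and total bilirubin are compared between groups as continuous outcomes, each will be analysed by ANCOVA of the log 72-hour value on treatment arm and log baseline value, and the adjusted ratio of geometric means will be reported with its 95% confidence interval. The unadjusted test may be kept as a sensitivity analysis.

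The t-test and Mann-Whitney wording can stay for other continuous variables, and the chi-square and exact tests for proportions. The cost is that sentence and one degree of freedom per model. No new patient, visit or measurement is needed.

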### **Ethical consideration:**

An ethical approval will be obtained from ethical committee of Faculty of medicine Beni-Suef University.

All patients in study agree to participate of their own free will and that they have been fully informed regarding the procedures of the research project and any potential risks.

If any patient included in study want to withdraw, stop study in this patient immediately.

The study will start after approval of the research ethical committee and according to guideline of the Declaration of Helsinki.

